Malnutrition is common among cancer patients, with prevalence rates ranging from 16–40% at diagnosis and increasing to 40–80% during treatment, depending on factors such as age, cancer type, and treatment modality(Bossi *et al*, 2021; Kaegi-Braun *et al*, 2021). Tumor location plays a crucial role, with the highest malnutrition rates observed in pancreatic (66.7%), esophageal/gastric (60.2%), head and neck (48.9%), and lung (45.3%) cancers(Hébuterne *et al*, 2014; Bossi *et al*, 2021).

Nutritional status in cancer patients is intricately linked to clinical outcomes. Tumor and therapeutic interventions notably impact nutritional health(Webb *et al*, 2020; Kipouros *et al*, 2023). Malnutrition significantly affects treatment tolerance, morbidity, survival, and quality of life(Hébuterne *et al*, 2014; Liu *et al*, 2021; Garutti *et al*, 2023). It can lead to reduced nutrient intake, cachexia, and impaired treatment efficacy(Muscaritoli *et al*, 2019; Holdoway *et al*, 2023). Early nutritional interventions have been shown to mitigate adverse clinical outcomes and reduce 30-day mortality in at-risk patients(Muscaritoli *et al*, 2019; Schuetz *et al*, 2019; Kipouros *et al*, 2023).

Although the association between malnutrition and adverse clinical outcomes has been well established (Muscaritoli *et al*, 2019; Liu *et al*, 2021; Kipouros *et al*, 2023), the benefits of nutritional improvement reported in different studies remain inconsistent (Schuetz *et al*, 2019; Kaegi-Braun *et al*, 2021). On the one hand, nutritional status might vary considerably over the course of treatment(Webb *et al*, 2020); on the other hand, psychological factors, sleep quality, and physical activity may further influence these outcomes (Nissim *et al*, 2024; Ye *et al*, 2024). High-quality and large-scale cohort studies that can capture dynamic changes in nutrition are needed to carry out more precise nutritional interventions or treatments to improve clinical outcomes. Hence, we established a cohort study to evaluate nutritional status and clinical outcomes in patients with common malignancies (NCOM study), aiming to provide evidence for personalized and precise nutritional treatment in oncology care.

53 **Methods**

54 **Study design**

55 The NCOM study is a multicenter, prospective cohort study designed to assess longitudinal
56 changes in nutritional status and their impact on clinical outcomes in cancer patients. We aim

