The sample size for the NCOM study was determined on the basis of the impact of nutritional status on clinical outcomes in cancer patients, with a two-sided significance level (α) of 0.05 and 80% power ($1 - \beta = 0.80$) (von Elm *et al*, 2007; Arends *et al*, 2017). On the basis of previous studies on nutritional status and cancer outcomes, we assumed a baseline event rate of 20% ($P_1 = 0.50$) in the unexposed group and an expected rate of 24% ($P_2 = 0.40$) in the exposed group (Rasschaert *et al*, 2024). Given that longitudinal oncology cohort studies report attrition rates ranging from 30% to 50% over a multiyear follow-up period (Reeves *et al*, 2007; Schwedhelm *et al*, 2016), the final target sample size for this study was estimated to be approximately 1,538 participants.

Data collection

Data collection followed a standardized protocol across all participating hospitals to ensure consistency and accuracy. The baseline assessments will be conducted within 48 hours of hospital admission, and well-trained researchers will collect information on demographic and clinical data, nutritional status, laboratory biomarkers, quality of life, psychosocial factors, physical activity, sleep status, and knowledge, attitudes, and practices (KAPs). Follow-up assessments will be conducted at predefined intervals to track longitudinal changes in nutritional status and clinical outcomes.

To ensure data reliability, each hospital will designate 1 to 2 trained personnel to be responsible for questionnaires and clinical data recording. At the same time, a supervisor will be appointed to review the integrity of the data and coordinate follow-up work if necessary. All researcher personnel

must complete standardized training and pass competency assessments to ensure consistency in data collection and minimize variations.

Data management will be centralized through the Research Electronic Data Capture (REDCap) system, which ensures data security, accuracy, and accessibility(Harris *et al*, 2009). Standardized, validated measurement tools will be used at each site. Data entry will include built-in validation checks to identify missing values or inconsistencies, with routine audits and cross-site comparisons performed to maintain high data quality and study validity.

Data Content & Assessment Tools

Demographics & Clinical Data

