Secondary analyses will investigate associations between nutritional status and psychosocial factors (e.g., EORTC QLQ-C30, HADS, PSQI) via paired t tests, mixed-effects models, and correlation analyses (Spearman or Pearson, depending on distribution).

To minimize bias and confounding factors, propensity score matching (PSM) will balance baseline differences between exposure groups. Multiple imputation will handle missing data to prevent systematic bias, and sensitivity analyses will exclude cases with extreme values, incomplete follow-ups, or protocol deviations.

Subgroup analyses will stratify findings by cancer type, treatment modality, and nutritional status category. Interaction terms are included in regression models to identify potential effect modifications, with exploratory analyses conducted if unexpected patterns arise.

By integrating multivariate modeling, survival analysis, repeated measures approaches, and

missing data imputation, this study ensures robust, high-quality, evidence-based insights into the impact of nutritional status on clinical outcomes and survival in cancer patients.

Informed Consent Process

Participation in this study is voluntary, and individuals may withdraw at any time without affecting their medical care. Before enrollment, participants and their families will receive detailed study information, including their purpose, methodology, potential risks, and benefits. A written informed consent form must be signed, confirming their understanding and voluntary participation.

The informed consent process will be conducted by trained research personnel, ensuring that participants fully understand the study's objectives and procedures; are aware of their right to withdraw at any time without impacting their current or future medical treatment; and have the opportunity to ask questions and receive clarifications before signing.

To accommodate diverse literacy levels, consent materials will be provided in clear, accessible language, with verbal explanations when needed. The informed consent form included both English and Chinese versions (**Supplementary File 1**).

Data Privacy & Confidentiality

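### The 80% power holds only for two equal exposure groups analysed in full; it allows neither for an unequal exposure split nor for patients dropped by the planned propensity score matching

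*Protocol*

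**What the plan says.** The Sample size section of the protocol plans for a "two-sided significance level (α) of 0.05 and 80% power". It gives each event rate twice, with different values: a "baseline event rate of 20% ($P_1 = 0.50$) in the unexposed group" and an "expected rate of 24% ($P_2 = 0.40$) in the exposed group". It cites "attrition rates ranging from 30% to 50% over a multiyear follow-up period" and concludes that the target is "estimated to be approximately 1,538 participants". It mentions neither the proportion of patients expected to be exposed nor matching.

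The Statistical analysis plan section makes multivariable regression the primary outcome analysis, adjusted for age, sex, stage, treatment modality, socioeconomic status and baseline KPS. After the secondary analyses it adds, as a measure against bias and confounding, that "propensity score matching (PSM) will balance baseline differences between exposure groups". It does not say which analysis the matched set feeds. The sensitivity analyses are named separately in the next sentence, and matching is not among them.

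For the likely exposure split, the Introduction gives malnutrition "prevalence rates ranging from 16–40% at diagnosis and increasing to 40–80% during treatment", and tumour-specific rates of 66.7%, 60.2%, 48.9% and 45.3%.

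**The concern.** In a cohort the exposure split is observed, not allocated. For a fixed total, a two-group comparison has close to its greatest power when the groups are equal, and the power falls as they become unequal. Matching can then remove patients as well: in 1:1 matching without replacement, every unmatched patient in the larger group is dropped.

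The protocol states one power figure and names two controls for confounding, regression and matching. The figure fits neither unless about half the cohort is exposed. At stake is the reading of a null result. An adjusted or matched comparison with real power well below 80% could be taken as evidence that nutritional status does not matter, on the strength of a power statement that does not describe it.

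**Working it through.** **Inputs.** From the Sample size section: two-sided alpha 0.05, power 80%, rates 0.50 (unexposed) and 0.40 (exposed), attrition 30% to 50%, target 1,538. From the Introduction: exposure prevalence f. Assumed here: exposure in two levels, 1:1 or 1:2 matching without replacement, everyone in the smaller group finding a match (best case), and no gain from within-pair correlation.

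**Step 1: reproduce 1,538.** With unpooled variance,

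n per group = (0.50×0.50 + 0.40×0.60) × (1.960 + 0.842)² / 0.10² = 384.6

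Two groups give 769.2 evaluable, and 769.2 / (1 − 0.50) = 1,538. The pooled formula gives 388 per group and 1,552 enrolled, which is close. Attrition of 30% gives about 1,099 to 1,109. The worded rates of 20% and 24% give about 6,719 to 6,732 at 50% attrition. So the target rests on 0.50 vs 0.40, 50% attrition and equal groups.

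**Step 2: formulas at prevalence f, with N evaluable.** Exposed e = f×N and unexposed u = (1 − f)×N.

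- Full cohort: power = Φ(0.10 / √(0.25/u + 0.24/e) − 1.96)
- 1:1 matched: m = min(e, u) pairs; power = Φ(0.10 / √(0.49/m) − 1.96)
- 1:2 matched: the full-cohort formula, with the larger group cut to at most 2m

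**Step 3: worked case, f = 16%, N = 769.** e = 123 and u = 646.

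- Full cohort: standard error √(0.25/646 + 0.24/123) = 0.0483; Φ(2.07 − 1.96) = 54%.
- 1:1 matched, 123 pairs: standard error √(0.49/123) = 0.0631; Φ(1.58 − 1.96) = 35%.
- 1:2 matched, 123 and 246: standard error √(0.25/246 + 0.24/123) = 0.0545; Φ(1.84 − 1.96) = 45%.

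**Step 4: results for N = 769 (50% attrition).**

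| Exposed | Pairs (1:1) | Full cohort | 1:1 matched | 1:2 matched |
|---|---|---|---|---|
| 16% | 123 | 54% | 35% | 45% |
| 30% | 231 | 73% | 58% | 71% |
| 40% | 308 | 79% | 71% | 79% |
| 45.3% | 348 | 80% | 76% | 80% |
| 48.9% | 376 | 80% | 79% | 80% |
| 66.7% | 256 | 75% | 63% | 75% |
| 80% | 154 | 61% | 43% | 53% |

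At 40% exposed there are fewer than two unexposed patients per exposed patient (461 against 2×308 = 615), so 1:2 matching can keep everyone in the best case. Pooled-variance power agrees to within about one point.

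**Step 5: split the fall into its two parts.** At 16% exposed, unequal groups alone take power from 80% to 54% (26 points), and 1:1 matching takes 19 more. At 40% the two parts are about 1 and 8 points.

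**Step 6: attrition of 30%.** N = 1,538 × 0.70 = 1,077. Power with 1:1 matching is 47% at 16% exposed (172 pairs) and 84% at 40% (431 pairs).

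**The case against.** The strongest reply is that matching is not the primary analysis. The protocol gives that role to adjusted regression, which needs no matching and can use every evaluable patient. This stands. A reader might infer from the sentence on matching that the main result will come from matched pairs, and so that the study as a whole has 35% to 71% power. The documents do not support that, because the role of the matched set is left open.

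Three further replies also stand.

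- The cap at twice the smaller group holds only for 1:1 matching without replacement. The protocol fixes no ratio, caliper or replacement rule. Such details commonly belong in a statistical analysis plan, and their absence is not criticised here.
- Matching cannot be blamed for the whole shortfall: at 16% exposed, the larger part comes from the unequal groups.
- It would be wrong to say that matching discards a large share at every prevalence the protocol quotes. With 1:1 matching the best-case loss is 68% of evaluable patients at 16% exposed, but about 9% at 45.3% and 2% at 48.9%. Exposure classes are also updated at each follow-up, and the during-treatment range of 40% to 80% includes an even split.

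A reader might add that the three mPG-SGA classes force separate matching for each pair of classes. The sample size compares two groups and NRS-2002 is binary, so the protocol does not commit itself to that.

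None of this rescues the stated power. The full-cohort regression avoids the matching loss but not the loss from unequal groups, and the protocol itself states 80% without naming a split.

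**Conclusion.** The point holds as a mismatch between the stated power and the planned comparisons. The 80% is correct for about 385 analysed patients in each of two equal groups, and the protocol gives no reason to expect that split. Over its own at-diagnosis range the shortfall is between about 1 and 26 points for the full cohort, and between about 9 and 45 points for a 1:1 matched set.

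These sizes rest on the 0.50 and 0.40 rates, on a simple two-proportion test as a stand-in for the adjusted model, and on complete matching. Patients without a close match would lower matched power further. Lower attrition would raise it: at 30% attrition and 40% exposed, the matched comparison exceeds the target.

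The contradiction in the event rates is a separate and larger problem. At 20% vs 24%, 769 evaluable patients in equal groups give about 27% power before any split or matching is considered. Nor do the documents show that matching is an unsound choice: matching, weighting and regression are all accepted methods, and the fault lies in the power statement.

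**What to change.** 1. Reconcile the worded and symbolic event rates in the Sample size section first, since every power figure depends on them.
2. In the Statistical analysis plan section, state that covariate-adjusted regression on all evaluable patients is the main confounding-controlled comparison, and label propensity score matching a sensitivity analysis. Propensity weighting on the full cohort is an option, not a requirement.
3. Whether or not matching is kept, state the expected exposure split and restate the power for it. Changing the method alone would leave the 80% unsupported.
4. If any main conclusion is to rest on the matched set, also give the power for the expected number of pairs. With 1:1 matching and 769 evaluable patients, that is at most about 123 to 308 pairs at 16% to 40% exposed.

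The cost is a few sentences and a less favourable stated power. No extra patients or data are needed.

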At each follow-up visit, trained personnel will actively assess AEs by reviewing medical records and laboratory findings, while participants will be encouraged to self-report symptoms between visits. Serious adverse events (SAEs), including hospitalization, prolonged disability, or life-threatening conditions, will be reported following institutional and ethical guidelines.

All AEs and SAEs are classified by severity, duration, and potential causality, with standardized

procedures for data entry, review, and risk assessment. Necessary medical interventions or protocol adjustments will be implemented as needed. This structured monitoring system will increase patient safety, reduce risks, and provide insights into the impact of nutritional interventions on clinical outcomes.

Follow-up assessments and data collection timeline

Follow-up assessments will be conducted at predefined intervals to track longitudinal changes in nutritional status, clinical outcomes, and survival trends. In the first year, participants will be closely monitored at 1, 2, 3, 6, and 12 months to assess early nutritional changes and treatment-related complications. Afterward, annual follow-ups will continue for an additional four years or until death or loss to follow-up, with a focus on survival status and disease progression. In-person hospital visits will be prioritized for follow-up to ensure a comprehensive evaluation of nutritional status, clinical outcomes, and quality of life (**Table 1**). If in-person visits are not feasible, telephone follow-ups serve as an alternative. Research personnel will document each follow-up attempt, including the method of contact, date, and details of the interaction. To minimize loss to follow-up, participants missing scheduled visits were contacted up to three times via phone calls or text messages. If a participant remains unreachable after three attempts, they will be classified as lost to follow-up, and their last recorded assessment will be used for analysis. Any known reasons for withdrawal, relocation, or health deterioration will be documented to ensure data transparency and completeness.

Variable	SV	Folllow-up						
		1 st month	2 nd month	3 rd month	6 th month	12 th month	Annually follow-up for another 4 years	

Demographics & Clinical Data	√						
KPS Scoring	√	√	√	√	√	√	√
mPG-SGA	√	√	√	√	√	√	√
NRS2002	√	√	√	√	√	√	√
Standardized anthropometric measurements	√	√	√	√	√	√	√
SDSAT	√	√	√	√	√	√	√

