Nutrition support in and out of hospital Nutrition support	√	√	√	√	√	√	√
Laboratory biomarkers	√	√	√	√	√	√	√
EORTC QLQ-C30	√	√	√	√	√	√	√
HADS	√	√	√	√	√	√	√
PSQI	√	√	√	√	√	√	√
Leisure-time physical activity levels	√	√	√	√	√	√	√
KAP Questionnaire	√				√	√	√
Short-Term Clinical Outcome		√	√	√	√	√	√
Long-term clinical outcomes		√	√	√	√	√	√
Adverse Event Recording	√	√	√	√	√	√	√

299 **Table 1.** Follow-up schedule. SV: screening visit; KPS: Karnofsky Performance Status; mPG-SGA:
 300 Subjective Global Assessment; NRS-2002: Nutritional Risk Screening 2002; SDSAT: Simple Diet Self-
 301 Assessment Tool; EORTC QLQ-C30: European Organization for Research and Treatment of Cancer

Quality of Life Questionnaire C30; HADS: Hospital Anxiety and Depression Scale; PSQI: Pittsburgh Sleep Quality Index; KAP : Knowledge, Attitude, and Practice.

Statistical analysis plan

Baseline characteristics are summarized as the means \pm standard deviations (SDs) for normally distributed variables, medians with interquartile ranges (IQRs) for skewed data, and percentages for categorical variables. For group comparisons (e.g., normal vs. mild malnutrition vs. moderate malnutrition patients), independent t tests or Mann–Whitney U tests were used for continuous variables, and chi–square tests or Fisher’s exact tests were used for categorical data.

The primary outcome analysis will apply multivariate regression models, adjusting for age, sex, cancer stage, treatment modality, socioeconomic status, and baseline Karnofsky Performance Status (KPS). Logistic regression was used to assess binary outcomes (e.g., nutritional risk, survival), whereas linear regression was used to evaluate continuous variables (e.g., BMI changes, weight loss percentage). To account for repeated measures, generalized estimating equations (GEEs) model longitudinal variations in nutritional status, biomarkers, and quality of life.

For survival analysis, Kaplan–Meier curves were used to estimate overall survival (OS) and progression-free survival (PFS), with log-rank tests used to compare groups. Cox proportional hazards models were used to explore the associations between nutritional status and survival outcomes, incorporating time-dependent covariates where applicable.

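### The sensitivity analysis that drops cases with incomplete follow-up selects on the outcome, so agreement with the main result would not show robustness to loss

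*Protocol*

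**What the plan says.** The Statistical analysis plan section handles missing data in one sentence. Its first half is "Multiple imputation will handle missing data to prevent systematic bias"; its second half is "sensitivity analyses will exclude cases with extreme values, incomplete follow-ups, or protocol deviations". The protocol does not define incomplete follow-up.

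Three other statements bear on the rule:

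- Follow-up assessments and data collection timeline, on when follow-up ends: "annual follow-ups will continue for an additional four years or until death or loss to follow-up".
- The same section, on patients who cannot be reached after three attempts: "they will be classified as lost to follow-up, and their last recorded assessment will be used for analysis".
- Sample size, on expected loss: "longitudinal oncology cohort studies report attrition rates ranging from 30% to 50% over a multiyear follow-up period".

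Survival is analysed by Kaplan–Meier, log-rank and Cox methods for OS and PFS, and by logistic regression for binary outcomes.

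**The concern.** Whether follow-up is complete is known only after baseline, and here it depends partly on the event. Death closes a patient's follow-up and makes the record complete. A patient who stays alive must be traced for five years to qualify. Restricting to complete cases therefore lets the outcome and its timing decide who enters the analysis.

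Kaplan–Meier and Cox methods already use a lost patient's event-free time through censoring. The exclusion discards that time and keeps the deaths. It does so in a study whose cited loss is 30% to 50%, which makes loss a leading threat to the conclusions.

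A robustness check should relax the assumptions of the analysis it checks. Standard multiple imputation allows loss to depend on observed data. The complete-case run needs completeness to be unrelated to the outcome given the model's covariates, which is a stronger requirement. Under this follow-up rule it fails for survival outcomes even when loss is random. Agreement between the two analyses would then be weak reassurance, and disagreement would be hard to interpret.

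**Working it through.** **Loss the plan was sized for.** The target of 1,538 can be reproduced from the rates given in symbols in Sample size (0.50 and 0.40), two-sided 0.05, 80% power, equal groups (assumed) and unpooled variance:

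2 × (1.960 + 0.842)² × (0.25 + 0.24) / 0.10² = 769.2; 769.2 / (1 − 0.50) = 1,538.4.

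The stated total thus fits 50% loss, the top of the cited range. The rates in words (20% and 24%) do not reproduce it; that contradiction is a separate matter.

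**Absolute risk.** Inputs: 5-year loss risk c = 30% and 50% (range from Sample size); 5-year mortality m = 40% and 50% (assumed). Deaths count as complete, hazards are constant, and loss is independent of death. Let D = −ln(1 − m) and L = −ln(1 − c).

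- Alive and traced to year 5: A = (1 − m)(1 − c)
- Death observed: E = (1 − A) × D / (D + L)
- Lost, hence excluded: 1 − A − E
- Mortality in the retained set: E / (E + A)

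For m = 0.40 and c = 0.30: D = 0.5108, L = 0.3567, A = 0.420, E = 0.580 × 0.5108 / 0.8675 = 0.3415. The estimate is 0.3415 / 0.7615 = 44.8%.

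| True m | c | A | E | Excluded | Estimate |
|---|---|---|---|---|---|
| 40% | 30% | 0.420 | 0.342 | 24% | 44.8% |
| 40% | 50% | 0.300 | 0.297 | 40% | 49.7% |
| 50% | 30% | 0.350 | 0.429 | 22% | 55.1% |
| 50% | 50% | 0.250 | 0.375 | 37.5% | 60.0% |

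At the protocol's worded rates of 20% and 24%, the same formula gives 23% and 28% at 30% loss, and 27% and 32% at 50% loss. In a simulation under the same assumptions, Kaplan–Meier with all patients kept and censored at loss recovers the true risks. The bias comes from the exclusion.

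**Association.** Take 40% mortality in one group and 50% in the other. The true odds ratio is (0.5/0.5) / (0.4/0.6) = 1.50 and the true hazard ratio is 0.6931 / 0.5108 = 1.36. The retained-set odds are E / A.

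- Equal loss, 30%: (0.4292/0.350) / (0.3415/0.420) = 1.51
- Equal loss, 50%: (0.375/0.250) / (0.297/0.300) = 1.52
- Loss 30% in the lower-risk group, 50% in the higher-risk group: 1.500 / 0.813 = 1.84
- Loss the other way round: 1.226 / 0.990 = 1.24

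Simulated Cox hazard ratios agree. With equal loss, about 1.36 becomes 1.35 (30% loss) or 1.32 (50% loss). With 30% versus 50% loss it becomes about 1.57 (1.56 to 1.58 across runs). For true risks of 20% and 24%, the hazard ratio moves from 1.22 (true 1.23) with all patients censored to 1.44 in the retained set under 30% versus 50% loss.

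**Loss related to prognosis.** True risks 20% and 24%, true odds ratio 1.26. Loss patterns are assumed.

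- 60% of exposed patients with events are lost and 35% of everyone else: (0.24 × 0.40) / (0.76 × 0.65) = 0.194 exposed, (0.20 × 0.65) / (0.80 × 0.65) = 0.250 unexposed; odds ratio 0.78.
- No deaths are lost, and 50% of exposed and 40% of unexposed survivors are lost: 0.24 / (0.76 × 0.50) = 0.632 and 0.20 / (0.80 × 0.60) = 0.417; odds ratio 1.52.

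The complete-case result can fall on either side of the truth.

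**The case against.** The strongest reply is that the study estimates associations, and these are largely preserved when loss is equal between exposure groups. In the 2×2 setting, the odds ratio is also unchanged when loss depends on exposure alone or on outcome alone. This stands, and it limits the claim: bias in absolute risk follows under the stated assumptions, while bias in the association needs differential or jointly dependent loss, for which the protocol gives no figures.

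It is also fair that a complete-follow-up subset beside an imputed analysis is a common descriptive comparison, that the protocol does not say in words that this run tests informative loss, and that it is not the primary analysis. A separate statistical analysis plan may add analyses, so the lack of a not-at-random analysis is not itself the point. The point is that the rule the protocol does state is biased if followed.

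Two stronger readings do not hold:

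- A reader might infer that only 5-year survivors would remain, so that no deaths could be seen. That requires death to count as incomplete follow-up, but the timeline section ends follow-up at death.
- A reader might infer that the protocol expects loss from worsening health. The sentence "Any known reasons for withdrawal, relocation, or health deterioration will be documented" is a recording rule and predicts nothing about how much loss has that cause.

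Nor can mortality be said to be overstated in every case. If deteriorating patients are lost and their deaths go unseen, the bias can run the other way.

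**Conclusion.** The concern holds in this bounded form. Under the protocol's own definition of when follow-up ends, excluding incomplete follow-up selects on the outcome. With constant hazards and loss independent of death, it raises estimated 5-year mortality by about 5 points at 30% loss and 10 points at 50% loss, for true mortality of 40% or 50%, and discards 22% to 40% of patients. Hazard ratios change little with equal loss and are materially distorted with 30% versus 50% loss.

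The mortality levels, the loss patterns by group and the independence of loss are assumptions; only the 30% to 50% range comes from the protocol. That range was taken as the loss risk in the absence of death. If it means the share of enrolled patients actually lost, the distortion of absolute risk under the same model is larger. Because incomplete follow-up is undefined, still more patients would be dropped if one missed visit counted. The main analysis is not invalidated, but this run cannot support a claim of robustness to loss. The change should be made.

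**What to change.** 1. Remove incomplete follow-up from the exclusion list for OS, PFS and the other longitudinal outcomes. Alternatively, keep a complete-follow-up run only as a labelled descriptive comparison, with the term defined and deaths counted as complete.
2. Keep all enrolled patients. Censor at the last-known-alive date for OS and at the last disease assessment for PFS.
3. As the robustness check, use two complementary analyses:
   - inverse-probability-of-censoring weights built from the nutrition, KPS, stage and treatment data already collected, for loss that measured data explain;
   - multiple imputation with a stepped delta adjustment, in which lost patients fare progressively worse than comparable observed patients, for loss that measured data do not explain. The weights alone cannot test this second kind of loss.
4. Report loss by exposure group, since differential loss is what moves the hazard ratio.

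The cost is a change of wording and modest extra programming. No additional patients or data are needed.
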